The University of Texas Medical Branch Galveston
Research Protocol

**Validating a New Method to Assess Estimated Blood Loss in the Obstetric
Population**

Principal Investigators: [name]
Co-Investigator: [name]
Faculty Sponsor: [name].
Funding: Department of Maternal Fetal Medicine

NCT03404375

1. Introduction/Background/Purpose:

According to the World Health Organization, postpartum hemorrhage (PPH) is the leading cause of maternal mortality in low-income countries and the primary cause of nearly one quarter of all maternal deaths globally (1). An estimated blood loss (EBL) in excess of 500 mL following a vaginal birth or a loss of greater than 1,000 mL following cesarean birth often have been used for the definition of postpartum hemorrhage, but the average volume of blood lost at delivery can approach these amounts when actually measured rather than estimated (2). More than half of all maternal deaths occur within 24 hours of delivery, most commonly from excessive bleeding (3). Worldwide, 140,000 women succumb to postpartum hemorrhage each year. The most common antecedents to postpartum hemorrhage are uterine atony, placental disorders, and trauma during delivery. Improving maternal health worldwide is one of the WHO's 8 Millennium Developmental Goals. The prevention and treatment of PPH is an essential step towards the achievement of that goal (4).

Estimates of blood loss at delivery are notoriously inaccurate, with under-estimation more common than over-estimation (5). Traditionally, the surgeon performing the cesarean section would estimate the blood loss by visually assessing the blood collected in the surgical drape and counting the number of lap sponges used thru out the procedure. Current detection and management of hemorrhage is heavily based on clinical judgment, which often leads to delay in recognition and intervention. Often, interventions such as fluid resuscitation and blood transfusion are not initiated until significant hemorrhage has already taken place. The traditional method for estimating blood loss is based on the surgeon and surgical staff's subjective assessment that is severely limited by human error and the presence of large volumes of amniotic fluid, irrigation, or both (6). Another limitation is that blood loss is frequently estimated at the end of the procedure.

Early detection and treatment of this potentially life threatening obstetric complication is of utmost importance in the field of obstetrics. Simulations and didactic training have been shown to improve visual estimations, but there are still poor associations between experience level and accuracy, and a

significant decay in blood loss estimation skills over time (7).

The Triton system (Gauss Surgical, Inc., Palo Alto, CA) is a novel mobile monitoring platform that combines mobile computing with Gauss Feature Extraction Technology (FET) to directly assess Hb mass (mHb) absorbed by surgical sponges from an image (8). The device is an iPad like imaging device that will assess blood loss via imaging of the surgical sponges used in the surgery. In 2014, Konig et al. showed that mobile blood loss monitoring using the Triton system is accurate in assessing mHb on surgical sponges across a range of ambient light conditions, sponge saturation, saline contamination, and initial blood Hb. Utilization of this tool could significantly improve the accuracy of blood loss estimates (9). Holmes et al. also showed that the novel mobile monitoring system provides an accurate measurement of mHb on surgical sponges as compared with manual rinsing measurements, and is significantly more accurate than the gravimetric method (10).

However, these studies were performed on patients undergoing a myriad of surgical procedures not just limited to obstetrical patients. To our knowledge, this technology has not been validated in the obstetrical population at risk for hemorrhage.

The gauss/triton colorimetric system is not standard of care at UTMB. Not enough data is available to support its use, despite being FDA approved to estimate blood loss. Most evidence is available in non-pregnant patients. In the obstetric population no definitive evidence exists, and the only trial that has been performed was recently published in AJP reports for which one of our co-PIs ([name]) is the chief editor (11). In that trial, only the accuracy was evaluated, and we believe that further evidence is needed to support its use.

Our hypothesis is that this device will enable clinicians to prospectively and objectively assess EBL. Ultimately after its validation, our results will be used to propose a multicenter clinical trial to the NICHD MFMU network to evaluate the clinical utility of this system.

This study will be a prospective cohort study, in which we will evaluate two methods of evaluating intraoperative blood loss during cesarean delivery (usual clinical assessment versus Device). Of note, the subjects consented will be used as self-controls.

- 2. Summary of project:** This study will be a prospective cohort study. Patients who are scheduled for an elective cesarean and meet criteria for inclusion in the study will be approached for participation at same day of admission. Written informed consent will be obtained from the patients by the Co-PI ([name]) and by the study collaborators ([name],

[name], [name], [name], and [name]). If patients agree to participate, a CBC (complete blood count) will be obtained via venous puncture. The device will be used during the delivery in the operating room. The device will be used to assess EBL by the research staff only and results/ EBL assessment will be masked to the clinical team. Unmasking will only occur after collecting the data from the device with purpose to perform data analysis. Patient management will be according to the clinical team. All patients undergo a CBC postpartum. The drop in Hgb (Δ Hgb) between the pre and post cesarean CBCs will be calculated for each patient. Patients will be divided into quartiles of Δ Hgb. Cases will be those patients whose Δ Hgb is in the upper quartile, while controls will be those patients whose Δ Hgb is in the lower 3 quartiles. We will be comparing EBL by standard clinical assessment versus result from the device between cases and controls.

The colorimetric Triton system which comprises of the device, software analysis and staff training will be supplied by the manufacturer free of charge. We will be offering our skills, fellows and residents, who will be collecting data and we will be performing the data analysis. Results will be available to the manufacturer after results are completed. The results of this study will be presented in conferences or published in a peer-review journal.

Demographic information will be obtained from the electronic medical record. The data will be kept on a password secured UTMB computer. An encrypted USB flash drive will be used to transfer data. The data will be identified and linked to the patient using the medical record number (MRN). During data analysis, all patient identifiers will be deleted.

3. Study procedures: VISIT#1

3.1 Screening, Recruitment and Consenting: When a patient meets inclusion criteria for participation in our study, the obstetrical team will contact the research team. Written informed consent will be obtained from the patient by the PI, study coordinator, or collaborator. Study participation will be complete when the patient is discharged from the hospital. The data collected will be kept on a password secured UTMB computer. An encrypted USB flash drive will be used to transfer data. The data will be linked via MRN, which is needed to access the demographic data and will be deleted when the data is analyzed. Our target sample size is 242 subjects.

3.2. Baseline procedures: In some patients, there will be no baseline procedures aside from using the masked device for assessment of EBL. If a preop CBC is not indicated clinically or not available, then a preop CBC will be obtained after consent is signed. Funding from the Ob/Gyn department will cover the cost of this test. The device will be set by the manufacturer not

to reveal the EBL in order to mask the surgical staff hence not affecting the standard assessment of EBL already implemented in our surgical suite. Neither the subject's insurance nor the subject will be responsible for any charges relating to tests done only for research. Please see attached budget and departmental letter of support.

3.3. Study visits/Follow-up: One study visit will be needed during the trial. The subject participation will be considered complete when the subject is discharged home.

3.6. Withdrawals: Subjects who withdraw from the study after inclusion will be excluded from further follow-up. Data collected until the time of withdrawal will be analyzed.

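### Cases are defined by a hemoglobin drop that includes bleeding after the operating room, which neither blood loss method can see; this modestly dilutes the comparison, and the plan has no analysis to show by how much

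*Combined protocol and SAP*

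**What the plan says.** **What the methods measure.** The last paragraph of Section 1 limits both to the operation: "we will evaluate two methods of evaluating intraoperative blood loss during cesarean delivery". The device is described there as one that will "assess blood loss via imaging of the surgical sponges used in the surgery", and Section 2 adds: "The device will be used during the delivery in the operating room". Section 3.2 calls the comparator the "standard assessment of EBL already implemented in our surgical suite".

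**What defines a case.** Section 2: "All patients undergo a CBC postpartum. The drop in Hgb (Δ Hgb) between the pre and post cesarean CBCs will be calculated for each patient". The upper quartile of that drop are cases and the other three quartiles are controls. No hour or window is given for the postpartum CBC.

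**Where the label is used.** It drives the primary outcome (Section 3.7: EBL in cases versus controls, by each method) and the ROC analysis (Statistical approach: AUC of each method for an upper-quartile drop). Section 3.7 lists post-partum hemorrhage, transfusion, uterotonics and colloid resuscitation as secondary outcomes, without separating onset during surgery from onset afterwards. The multivariable analysis names no covariates.

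**The concern.** The measurement window closes when the woman leaves the operating room. The reference window stays open until the postpartum CBC. Whatever time is chosen for that draw, the reference covers the longer period, so blood lost in between counts toward case status but cannot appear in either EBL.

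A woman with an unremarkable operation and a later bleed can thus be a case with a low EBL by both methods. Such women pull the case mean toward the control mean, lower both AUCs and narrow the gap between them. The practical cost is ambiguity: a disappointing AUC could reflect device error or blood the device was never shown, and no planned analysis tells these apart. Section 1 intends the results to support a proposal for a multicenter trial, so the distinction matters beyond this study.

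**Working it through.** **1. The plan's own figure.** Inputs from Statistical approach: difference 139 mL, SD 317 mL, two-sided alpha 0.05, power 0.80, ratio 1:3.

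n1 = (1 + 1/3) × (1.960 + 0.842)² × 317² / 139² = 1.333 × 7.849 × 5.201 = 54.4, so 55 cases and 165 controls, N = 220. The exact t test gives power 0.801. The stated 242 is 220 × 1.10. The figure reproduces. It contains no stated allowance for cases that arise from later bleeding.

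**2. Size of the dilution.** The documents give no rate or volume of bleeding after the operating room, so this is an illustration. Simulation of 400,000 women:

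- Intraoperative loss is lognormal with mean 555.8 and SD 317 mL (Statistical approach).
- Hemoglobin-drop index = intraoperative loss + later loss + noise, with the noise set so that the correlation with intraoperative loss is 0.7 (or 0.5) when there is no later loss. *Assumed.*
- Measurement error SD is 100 mL for the device and 300 mL for the clinical estimate. *Assumed.*
- The top quartile of the index are cases. A case counts as created if she would not have been in the top quartile without the later loss.

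Results at correlation 0.7:

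| Later bleeding (assumed) | Later bleeders among cases | Cases created | True case-control difference | Device AUC | AUC gap, device minus clinical |
|---|---|---|---|---|---|
| None | 0% | 0% | 405 mL | 0.82 | 0.076 |
| 5% lose 500 mL | 13% | 8% | 393 mL | 0.81 | 0.073 |
| 10% lose 500 mL | 25% | 15% | 382 mL | 0.80 | 0.070 |
| 10% lose 800 mL | 34% | 24% | 352 mL | 0.77 | 0.060 |

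From unrounded values, device AUC falls by about 0.01 to 0.05 and the gap by about 0.004 to 0.016. Repeat runs differ by a few mL and about 0.001 in the gap. At correlation 0.5 the difference falls from 292 mL to 284 mL (10%, 500 mL) or 271 mL (10%, 800 mL).

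The third and second columns differ because many later bleeders would have been cases anyway. With 10% losing 500 mL, about 39% of the later bleeders who are cases qualify without the later loss: 25% × (1 − 0.39) = 15%.

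**3. Against the precision of the study.** The standard error of the case-control difference at 55/165 is 317 × √(1/55 + 1/165) = 49.4 mL. The planned difference is 139/49.4 = 2.8 standard errors. The smallest difference above is 271/49.4 = 5.5. For the clinical estimate, with its extra error, SD = √(317² + 300²) = 436 mL and the standard error is 436 × 0.1557 = 67.9 mL, so 271/67.9 = 4.0. The primary comparison is not in danger in this model. One AUC of 0.82 at 55/165 has a standard error of about 0.037, so the loss of AUC runs from about a third of a standard error to somewhat more than one.

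**4. Would a sensitivity analysis recover it?** Removing all women with later loss and re-deriving the quartile restores 405 mL (correlation 0.7) and 292 mL (correlation 0.5). That assumes a perfect flag.

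**The case against.** The best case against the point is that it is small and rests on an assumed rate. The population is scheduled cesareans with previa and known placental anomalies excluded, so 10% losing 500 mL or more before the CBC may be high. With 5% losing 500 mL, the difference moves by only about 5 to 12 mL. All of this stands, and it limits the claim to modest dilution.

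It can also be said that the stated ROC target is an upper-quartile drop, so these women are correctly labelled under the plan. That is true, and they should not be called mislabelled. The target still does not match what the methods are said to measure.

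A third objection is that Section 3.7 already collects post-partum hemorrhage and transfusion. It does, but not by time of onset, and nothing links them to the case-control comparison.

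Several stronger readings are tempting and not supported:

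- *Women who bleed on the ward become cases that both methods miss.* They can, if the bleed precedes the CBC and is large enough. With 10% losing 500 mL, the later bleeders who are cases still average about 653 mL intraoperatively, against 459 mL in controls, so many remain detectable.
- *A quarter to a third of cases are false.* The 25% and 34% count every later bleeder among cases. The created share is 15% and 24%.
- *Power falls to 0.71 or 0.61.* Those values follow if 10% or 20% of cases have control-level EBL and the undiluted difference is exactly 139 mL, giving 125.1 or 111.2 mL. The model above contradicts both conditions.
- *The comparison favours one method.* Both face the same reference.
- *Section 1 shows that later bleeding is common.* The sentence "More than half of all maternal deaths occur within 24 hours of delivery, most commonly from excessive bleeding" concerns deaths and does not separate bleeding in the operating room from bleeding afterwards.

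**Conclusion.** The mismatch is in the text and nothing in the plan corrects it: both methods cover the operation only, while case status depends on all loss up to an untimed postpartum CBC. It dilutes the case-control difference, both AUCs and their gap. In the assumed range, 8% to 24% of cases are created this way, device AUC falls by about 0.01 to 0.05 and the gap by about 0.004 to 0.016.

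These sizes rest on assumed bleed rates, volumes, correlation and error SDs, none of which the documents supply. The large margin over 139 mL likewise depends on a correlation of 0.5 to 0.7. The correlation between EBL Device and EBL Standard does not use the hemoglobin drop and is unaffected. The point bears on how the AUCs can be interpreted; it does not show that the primary analysis fails. It is worth acting on because the rate is unknown and recording it is cheap.

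**What to change.** Keep the primary analysis and the sample size. Add the following to the plan:

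1. Before device data are unmasked, abstract from the chart the time of the postpartum CBC used for the hemoglobin drop, and a yes/no flag for documented bleeding between leaving the operating room and that CBC. Define in advance what counts.
2. Pre-specify one sensitivity analysis that removes flagged women, re-derives the upper quartile in the rest, and repeats the case-control EBL comparison and both AUCs.
3. Report post-partum hemorrhage by onset: intraoperative or after the operating room.

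The cost is a small addition to chart abstraction from records already in use, and one repeat analysis on slightly fewer women. The correction is partial: a chart flag misses unrecognised bleeding and ordinary undocumented postoperative loss, so the report should state that limit.

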3.7 Outcomes

- **Primary outcome:** Differences in EBL between cases and controls using clinical estimate versus device assessment.
- **Secondary outcomes: System performance (ROC sensitivity analysis and correlation).** Delta hemoglobin, transfusion requirements, administration of uterotonics, colloid resuscitation, post-partum hemorrhage or hemorrhagic shock.

4. Criteria for inclusion of subjects:

Pregnant women between the ages of 18-50.
Scheduled cesarean delivery.

5. Criteria for exclusion of subjects:

- Incarcerated patients
- Patient unwilling or unable to provide consent
- Intrauterine fetal demise (no fetal heart beat identified and documented by two physicians)
- Placenta previa or other known placental anomalies
- Enrolled in another trial that may affect outcome.

6. Sources of research material: Electronic medical records.

7. Recruitment methods and consenting process: See 3.1 above.

8. Potential risks

8.1 Loss of confidentiality: Any time information is collected, there is a potential risk for loss of confidentiality. Every effort will be made to keep the subject's information confidential; however, this cannot be guaranteed.

9. Potential benefits: With this novel approach of assessing blood loss more objectively during cesarean section, there are many potential benefits,

including: decrease in the delay in diagnosis of hemorrhagic shock, decrease in delay in interventions and improved postpartum surveillance. In addition, this data will be useful in designing a level 1 trial to measure outcomes such as transfusion rates, transfusion complications, hemorrhage and maternal death.

10. Data monitoring: The PI, research coordinator, and collaborators will ensure that all aspects of data quality adhere to the study design. This will include monitoring for adherence to consent procedures, inclusion and exclusion criteria, valid abstraction, correct entry, timeliness and responsiveness to data queries. Data will be collected and stored with the participant ID code only. The master enrollment log linking patient identifiers with study ID numbers will be kept in a password protected database on the Ob/Gyn department's internal server. Several data collection forms will be used. Data on these forms will be devoid of personal identifiers and will be securely stored at the division offices. The research coordinator will be available to monitor the data and correct any discrepancies based on source documents if needed.

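### Case status is the raw hemoglobin drop with no allowance for transfusion, so a heavy bleeder transfused before the postpartum CBC can be counted as a control; probably few women are affected, but no stated analysis would show it (minor)

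*Combined protocol and SAP*

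**What the plan says.** Section 2 (Summary of project) defines the grouping variable as the Hgb drop, which "between the pre and post cesarean CBCs will be calculated for each patient". Women in the top quartile of that drop are cases and the lower three quartiles are controls. The Statistical approach section repeats the rule and uses the same top quartile as the target of the ROC analysis. Neither place mentions transfusion.

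On care and timing, Section 2 says "Patient management will be according to the clinical team. All patients undergo a CBC postpartum". No time is given for the postpartum CBC, absolute or relative to transfusion. Section 3.2 covers the other end of the interval: "If a preop CBC is not indicated clinically or not available, then a preop CBC will be obtained after consent is signed".

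The plan foresees that transfusion can happen, since the secondary outcomes in Section 3.7 include "transfusion requirements, administration of uterotonics, colloid resuscitation, post-partum hemorrhage or hemorrhagic shock". It does not connect transfusion to the case definition, the exclusions or any analysis. The multivariable analysis names no covariates.

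Two features point to a low transfusion rate. Recruitment is of "Patients who are scheduled for an elective cesarean and meet criteria for inclusion in the study", and Section 5 excludes "Placenta previa or other known placental anomalies".

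**The concern.** Transfusion raises Hgb. A woman who bled heavily and received blood between the two CBCs can show a small net drop and fall into the lower three quartiles. Because cases are a fixed quarter of the sample, a woman with a smaller true fall takes her place. The women at risk of this are the ones a validation of blood-loss measurement most needs to classify correctly.

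The quartile of Hgb drop is the only reference standard for the primary contrast and for the AUC comparison, so no other part of the plan would reveal the error. Adding transfusion as a covariate would not repair a wrong case label or a wrong ROC target.

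Not every transfused woman is displaced. Some would have been controls anyway, some remain cases despite the transfusion, and none is displaced if the CBC precedes the transfusion.

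**Working it through.** **1. The plan's own figure.** Inputs from the Statistical approach section: means 555 and 416 mL (gap 139), common SD 317, two-sided alpha 0.05, groups of 55 and 165. The standard error is 317 × √(1/55 + 1/165) = 49.4 mL and the noncentrality is 139/49.4 = 2.82. Power from the noncentral t is 0.801, so N = 220 reproduces. The target of 242 is 220 × 1.10.

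**2. Cost of displaced women.** Suppose each displaced case lost L mL and is replaced among the cases by a woman at the control mean of 416 mL, with the SD held at 317. With k displaced, the gap becomes 139 − k × (L − 416) × (1/55 + 1/165). The loss per woman is 139 × 0.02424 = 3.4 mL at L = 555, 334 × 0.02424 = 8.1 mL at L = 750, and 584 × 0.02424 = 14.2 mL at L = 1,000. The values of L are assumptions: 555 is the planned case mean, 1,000 is the cesarean hemorrhage threshold in Section 1, and 750 lies between.

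| L (mL) | k = 1: gap, power | k = 2: gap, power | k = 3: gap, power |
|---|---|---|---|
| 555 | 135.6, 0.78 | 132.3, 0.76 | 128.9, 0.74 |
| 750 | 130.9, 0.75 | 122.8, 0.70 | 114.7, 0.64 |
| 1,000 | 124.8, 0.71 | 110.7, 0.61 | 96.5, 0.50 |

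**3. If nobody is lost.** With all 242 women evaluable (about 60 and 182), 1/60 + 1/182 = 0.02216 and baseline power is 0.83. One displaced woman at 555 mL takes off 3.1 mL (gap 135.9, power 0.82). One at 1,000 mL takes off 12.9 mL (gap 126.1, power 0.76).

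**4. If the true gap is larger.** With 55 and 165 and an assumed gap of 180 mL, baseline power is 0.95. One woman displaced at 1,000 mL leaves 0.92, and three leave 0.79.

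**5. How many women might move.** This was simulated with 220 women and 55 cases, 6,000 runs per scenario. From the document: EBL mean 555.8 and SD 317. Assumed: lognormal EBL, equal error for both methods (SD 0.35 on the log scale), Hgb-drop SD 0.8 and pre-op Hgb 11.5 (SD 1.0) g/dL, a correlation of 0.33 between drop and true loss (gap about 140 mL, power 0.80), 1, 2 or 4 women transfused before the CBC, and a rise of 1–2 g/dL. When transfusion goes to the women with the greatest true loss or the highest clinical EBL, one transfused woman displaces 0.3–0.8 cases on average and four displace 1.6–3.1. Power with 1, 2 and 4 transfused:

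- greatest true loss: 0.69–0.74, 0.60–0.69, 0.43–0.57
- highest clinical EBL: device 0.73–0.76, 0.68–0.72, 0.60–0.66; clinical 0.66–0.70, 0.54–0.61, 0.33–0.48
- Hgb trigger: 0.78–0.80, 0.76–0.79, 0.73–0.79

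**6. Device versus clinical AUC.** The difference shifts toward the device only when the clinical EBL drives transfusion: about +0.001 with one woman, +0.003 with two, and +0.004 to +0.007 with four. Otherwise it stays within simulation noise (0.001) of zero.

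**7. Behaviour of the two sensitivity analyses** (described under the fix). Against an undisturbed gap of 140 mL, excluding the transfused women gave 106–139 mL and adding them as cases gave 136–186 mL. The AUC difference, zero by construction, was −0.001 to +0.002 with exclusion and −0.008 to +0.001 with addition.

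**The case against.** The strongest objection is that nothing in the documents shows that any woman would be misclassified. There is no transfusion rate, trigger, Hgb rise or CBC time, and the cohort is low risk. This stands, and it limits the point to a possibility.

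The low power figures in step 5 also depend on the trigger. The true-loss scenario always transfuses the heaviest bleeders. With one woman transfused, those displaced averaged about 1,580–1,590 mL on the device, well above the 1,000 mL used in step 2. Under an Hgb trigger little is lost. The 139 mL gap is itself an assumed 25% effect, and enrolling 242 cushions one displacement. All of this stands.

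Each woman is measured by both methods, so both face the same labels and their comparison barely moves. The planned Pearson correlation between methods does not use Hgb at all. That also stands.

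Three stronger readings are tempting. A reader might infer that the study is underpowered or its reference standard invalid, but that needs several displaced heavy bleeders, which the documents do not establish. Section 1's remark about late transfusion is general background, not a description of this cohort. A reader might infer that the comparison is biased toward the device, but a shift of at most about 0.007 under one assumed trigger does not support that. A reader might infer that the secondary outcome delta hemoglobin is mismeasured. It is a valid observed laboratory change and needs only context.

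What the objection does not remove is that the case rule is stated twice without a transfusion provision, and a reader of the results could not tell whether it mattered.

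**Conclusion.** The point holds as a minor one. The stated rule can label a transfused heavy bleeder a control in the primary contrast and in the ROC reference standard, and the plan has no analysis that would detect it. The effect is nil if nobody is transfused between the CBCs. One displaced woman costs between about 2 and 9 points of power at 220 (0.80 to 0.78 or 0.71, for losses of 555 and 1,000 mL), and between about 2 and 8 points at 242 (0.83 to 0.82 or 0.76). Larger losses of power need several displaced women, or a trigger that always selects the heaviest bleeders. These sizes rest on the planned gap and SD, a replacement at the control mean, and assumed losses for the displaced women.

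**What to change.** Keep the stated quartile rule as the primary classification. From the medical record, note the time of the postpartum CBC and of any transfusion, and report how many women were transfused between the two CBCs. If there were none, one sentence closes the matter.

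To cover the case where there are some, prespecify two repeats of the primary contrast and the AUC comparison. Do this before the device results are opened; Section 2 already marks that moment: "Unmasking will only occur after collecting the data from the device with purpose to perform data analysis".

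- (a) Exclude these women and re-form the quartiles among the rest.
- (b) Keep the stated cases and add these women as cases.

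State in advance that (a) tends to shrink the case-control gap and (b) tends to enlarge it, and that (b) can favour the clinical estimate if that estimate prompted transfusion. A change in the size of the gap alone is therefore not grounds to limit the conclusion. Limit it only if the direction, or the result at the 0.05 level, of the device-versus-clinical comparison under (a) or (b) differs from the primary analysis. Report delta hemoglobin with and without these women for context.

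The cost is two times per chart and, if needed, two repeated analyses. The plan already names "Sources of research material: Electronic medical records" and already lists transfusion as a secondary outcome. The primary rule, sample size, blood tests and patient care stay as they are.
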